##### 9.4.2 Sample Submission Schedule

Stool samples will be collected at the following time points

- Less than 5 days prior to treatment with combined checkpoint inhibitors.
- Three weeks or C1W4 (+/- 5 days) of therapy
- At the time of disease progression or at the end of the study

##### 9.3.3 Sample Preparation Guidelines

All samples will be processed locally at each participating institution according to the laboratory manual (see Section 9.4). Stool samples in Omniprep®-Gut kits will be stored at -80°C freezer at each participating institution. Specimen will be batched and shipped on dry ice overnight to GU-LCCC HTSR (attn. [name]) at the end of the study first, then batched & shipped to [name] at MD Anderson Cancer Center.

## **10.0 STATISTICAL CONSIDERATIONS**

### **10.1 Design and Objectives**

All patients who meet eligibility criteria and enroll in the trial will receive the same nivolumab in combination with ipilimumab followed by nivolumab monotherapy regimen following the FDA approved schedule. Patients whose tissue block is not evaluable, either due to failure to be received by the GU-LCCC MRFBC Mucosal and Acral Lentiginous Melanoma Tissue Bank or due to insufficient tumor on the block, will be replaced.

The primary objective of this trial is to determine if treatment with nivolumab in combination with ipilimumab would produce ORR greater than historical 23% response rate in patients with MCM who received anti-PD1 monotherapy. Secondary objectives are to determine ORR, PFS and OS in each cohort, evaluate MCM and ALM genomic landscape by using whole exome sequence profiling and identify frequency of somatic mutations and relationship to tumor response, identify specific driver mutation in MCM and ALM. Exploratory objectives are to evaluate whether pre-existing immune cell infiltrates and tumors at the invasive tumor margin could predict clinical response to the combination of nivolumab and ipilimumab, as previously suggested in cutaneous melanoma, evaluate tumor putative neoantigen epitopes and determine binding affinity to MHC class I molecules as a potential predictor of response to combined checkpoint inhibitors treatment. The study will also explore relationship of specific local microbiota in MCM and ALM and response or resistance to the combination therapy. The final exploratory objective is to determine clonal preservation, expansion, and selection of TCR rearrangement of TILs before and during treatment with combined immune checkpoint inhibitors therapy as a predictive biomarker for treatment response.

The primary endpoint is best overall response (complete or partial response as defined in Section 10.3.1); patients will be followed for progression-free and overall survival.

Patients who enroll in this trial but do not receive at least one dose of nivolumab in combination with ipilimumab, or those for whom tissue is not submitted (see section 9.2) and therefore cannot be classified into a predictive factor group, will be deemed unevaluable for the primary endpoint of the study; available information on these patients will be described in the final report.

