### 3.2 Ineligibility Criteria

- 3.21 Patients who do not have available tissue for immunohistochemistry and nucleic acids analyses.
- 3.22 Patients who have received prior immunotherapy for unresectable or metastatic disease.
- 3.23 Patients with evidence of active brain metastases, or active leptomeningeal disease are ineligible. Patients with a history of brain metastases must have completed treatment (i.e. surgery or radiation) prior to enrollment..
- 3.24 Patients with inadequate tissue for analysis.

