#### 9.2.1 Pathology Review

A total of 26 unstained FFPE tumor tissue will be stored at each institution after enrollment. At the end of the study, all samples, including on-treatment biopsy samples, at participating institution will be batched and shipped to the Histopathology Shared Resource at the G-LCCC. Pathologic diagnosis will undergo central review by study dermatopathologist. A provided Haematoxillin & Eosin stained slide will be used to confirm physical characteristics of tumor samples and eligibility for the correlative studies. The following criteria are required for molecular analyses based on the TCGA Biospecimen Qualification Criteria:

1. Tumor nuclei are presented in  $\geq 60\%$  of the slide
2. Tumor necrosis is  $\leq 20\%$
3. In the case of frozen tissue submission, the samples must be continuously frozen with less than 30 minutes between devascularization and freezing.

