## 10.2 Sample Size Considerations

The primary endpoint is objective response rate (CR+PR) as defined earlier in the metastatic MCM population. ORR in the ALM populations will be exploratory. The response rate with current standard therapy is approximately 23-25%(65). Secondary clinical endpoints include, median PFS and OS, 6 month landmark PFS and 1 year landmark OS. Biomarker exploratory endpoints will include: 1) the relationship of CD8 T cell score at the invasive margin and tumor response for each malignancy and 2) the relationship with tumor mutational frequency using whole exome sequencing and response. Bioinformatic tools will be used in an attempt to identify recurring driver mutations in MCM (as well as ALM).

The sample size is based on the primary endpoint objective response rate (ORR). The null hypothesis that the ORR is at most 25% will be tested against a one-sided alternative. If the ORR is less than 25%, we will consider this therapy not worth pursuing. If it is more than 25%, the therapy is considered worth pursuing. With 39 patients, the study would have 90% power at a significance level of 10% if the true ORR is 45%. To take into consideration a potential non-evaluable or dropout rate of 20%, 49 patients with MCM (cohort A) will need to be enrolled into this study. The exact binomial calculation is used.

Given the less frequent occurrence of metastatic melanoma involving ALM subtypes, we will plan to enroll only 24 patients with ALM (cohort B). This should allow the accrual to both cohorts to finish at roughly the same time. Analysis of activity Cohorts B and the biomarker data will be primarily descriptive and exploratory.

Patients who enroll in this trial but do not receive the immune checkpoint inhibitor combination, or those for whom tissue is not submitted (see section 9.0) and therefore cannot be classified into a predictive factor group, will be deemed unevaluable for the primary endpoint of the study; available information on these patients will be described in the final report.

The overall accrual rate is anticipated to be 2-4 patients per month on each cohort, based on past experience among each institution in the Melanoma Research Foundation Breakthrough Consortium , resulting in expected accrual duration of about 20-24 months. The trial's primary analyses are planned to occur at 6 months after each patient has received the treatment.

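### Tissue-based replacement and evaluability for the primary ORR are generally decided after the patient's response is known, and the stated tissue shipping times conflict

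*Combined protocol and SAP*

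**What the plan says.** **Replacement.** Section 10.1 gives two triggers. The first is non-receipt: "Patients whose tissue block is not evaluable, either due to failure to be received by the GU-LCCC MRFBC Mucosal and Acral Lentiginous Melanoma Tissue Bank". The second follows directly: "or due to insufficient tumor on the block, will be replaced".

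**Evaluability.** Sections 10.1 and 10.2 remove two groups from the primary endpoint: patients who do not receive the combination, and patients whose tissue is not submitted.

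**Where the tissue is.** Section 9.2.1 keeps it at the sites: "A total of 26 unstained FFPE tumor tissue will be stored at each institution after enrollment". It then says "At the end of the study, all samples, including on-treatment biopsy samples, at participating institution will be batched and shipped" to the central laboratory. The next step is "Pathologic diagnosis will undergo central review by study dermatopathologist", and an H&E slide "will be used to confirm physical characteristics of tumor samples and eligibility for the correlative studies".

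**Entry.** Section 3.1.3 requires a block or 26 slides with enough tumor for the planned assays. Section 3.2 excludes "Patients with inadequate tissue for analysis". Under Section 4.0 the coordinating center confirms eligibility from source documents.

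**Outcome.** Section 5.2 has the study investigators read response at about 12 weeks and about every 12 weeks after that. Section 10.2 expects 20-24 months of accrual and adds: "The trial's primary analyses are planned to occur at 6 months after each patient has received the treatment".

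**The concern.** A replacement rule is harmless if it is applied before anyone knows how the patient has done. Here the trigger rests on what the central bank receives and how much tumor it holds, and the bank gets the tissue late. Nothing in the plan dates the replacement decision, masks it to response, or caps it.

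This reaches the primary endpoint because tissue submission also decides who counts in the ORR. Submission is a site action, and the site's investigators read the response in a single-arm, open-label study. If tissue is missing more often for non-responders than for responders, for whatever reason, the ORR among evaluable patients is biased upward. The reverse pattern biases it downward.

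**Working it through.** **1. The plan's own figures (Section 10.2).** Inputs: null ORR 25%, alternative 45%, one-sided 10%, exact binomial, n = 39, 20% allowance.

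- Cut-off: the smallest r with P(X ≥ r | 39, 0.25) ≤ 0.10. At r = 13 the probability is 0.154; at r = 14 it is 0.0862. So r = 14.
- Power: P(X ≥ 14 | 39, 0.45) = 0.9048. No n from 30 to 38 reaches 0.90 (the highest is 0.8933, at n = 36).
- Enrollment: 39 / (1 − 0.20) = 48.75, rounded up to 49.

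The sample size reproduces.

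**2. The shipping times side by side.**

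| Place | Tissue reaches the bank | Against accrual | Against that patient's response |
|---|---|---|---|
| 9.2.1, 9.2.2, Appendix G table | End of the study | After accrual closes | After |
| Schema | End of participation | Some may fall within accrual | Generally after |
| Section 11, pathology form | End of the patient's treatment | Some may fall within accrual | Generally after |
| Appendix G footnote | Both end of the patient's therapy and end of the trial | Unclear | Generally after |

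Under the first row, replacement triggered by central receipt cannot happen while accrual is open. Under the other rows it can for some patients, but treatment runs until progression, intolerable toxicity or the dose maximum (Section 5.2). The block therefore usually travels after at least one response read. The exception is a patient who stops before the first scan.

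**3. Does the loss of tissue hurt power?** With 49 enrolled, no replacement, and the cut-off recomputed for each evaluable number:

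| Lost (assumed) | Evaluable n | Cut-off | Exact alpha | Power at 45% |
|---|---|---|---|---|
| 0% | 49 | 17 | 0.084 | 0.946 |
| 10% | 44 | 16 | 0.063 | 0.905 |
| 20% (plan) | 39 | 14 | 0.086 | 0.905 |
| 25% | 37 | 14 | 0.058 | 0.851 |
| 30% | 34 | 13 | 0.061 | 0.833 |

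Up to the planned allowance, power holds without replacing anyone.

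**4. How much could selection matter?** The documents give no tissue failure rate by response, so these rates are assumptions. Let N = 49, true ORR p = 0.25, and let qR and qN be the probabilities that a responder and a non-responder are excluded.

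- Evaluable ORR: p* = p(1 − qR) / [p(1 − qR) + (1 − p)(1 − qN)].
- Evaluable number m: binomial with N = 49 and the denominator above as its probability.
- Type I error: the sum over m of P(m) × P(X ≥ r_m | m, p*), where r_m is the exact 10% cut-off for m.

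Example: 0.25 × 0.85 = 0.2125 and 0.75 × 0.7833 = 0.5875, so p* = 0.2125 / 0.8000 = 26.6%.

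| qR | qN | Overall excluded | Expected evaluable ORR | Type I error |
|---|---|---|---|---|
| 20% | 20% | 20% | 25.0% | 0.073 |
| 15% | 21.7% | 20% | 26.6% | 0.111 |
| 10% | 23.3% | 20% | 28.1% | 0.160 |
| 5% | 25% | 20% | 29.7% | 0.219 |
| 25% | 18.3% | 20% | 23.4% | 0.045 |

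The second row is a small shift. Of 49 × 0.25 = 12.25 expected responders, 15% is 1.84 excluded, against 2.45 at 20%. That is about 0.6 of a patient.

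**The case against.** Several points on the other side are sound.

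- **Replacement is not impossible.** A reader might infer from Section 9.2.1 that nobody can be identified while accrual is open. The Schema, Section 11 and the Appendix G footnote do not support that as a general statement. With 20-24 months of accrual, some blocks could arrive in time under per-patient shipment.
- **Entry criteria help.** Adequate tumor is required by 3.1.3 and 3.24, and eligibility is confirmed centrally from documents. This should reduce failures. It does not remove them: no pathology read of adequacy before treatment is described, and Section 10.1 plans for failures.
- **The 60% nuclei and 20% necrosis limits are not the stated trigger.** Section 9.2.1 ties them to molecular analyses and correlative eligibility. Section 10.1 says only that tumor is insufficient and does not say who judges it.
- **The route into the ORR is narrow.** Sections 10.1 and 10.2 exclude patients whose tissue is not submitted. They do not say that submitted but insufficient tissue removes a patient, and they do not say that it does not.
- **Nothing shows that the central pathologist sees responses.** The plan is silent on masking; it does not describe an unmasked adequacy review.
- **The Laboratory Manual is a separate document that was not available.** It may hold a more exact shipping rule.

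These points limit the concern to timing and to the analysis set. They do not answer it, because no stated timing puts the tissue decision reliably before the response read.

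**Conclusion.** The point holds as a defect in how the primary analysis set is formed. The shipping times contradict one another, and under each of them replacement and tissue-based evaluability generally come after the patient's response is known.

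Two stronger conclusions are not supported. The first is that the trial is underpowered: the 49 already carries the 20% allowance, and 39 evaluable patients give 0.905. The second is that cohort A would have to reopen to replace the patients lost. Losing 10 of 49 leaves the planned 39, and the documents do not say how much of the allowance is tissue failure.

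The size of any bias cannot be derived from the documents. The 0.111 figure assumes that the full 20% leave the ORR set, at 15% of responders and 21.7% of non-responders, with no replacement. Exclusion unrelated to response gives 0.073, and the opposite imbalance gives 0.045. What the illustration shows is that a modest imbalance is enough to pass the planned 0.10. The defect can be corrected by amendment, and should be, because it touches the primary endpoint.

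**What to change.** 1. **Separate the ORR set from the tissue set (10.1 and 10.2).** Keep every eligible mucosal melanoma patient who received at least one dose of the combination in the primary ORR, whatever their tissue status. Amend the rule on unsubmitted tissue in both sections, and let tissue define only the biomarker set. State that the cut-off follows from the number in the ORR set, for example 17 responses if all 49 count.
2. **Reconcile the shipping times** across the Schema, 9.2.1, 9.2.2, Section 11 and Appendix G.
3. **Move the adequacy read forward.** Send the existing H&E slide or its scan for the central review already planned, at or soon after registration, to be read without response data. Quarterly batches would not do: a patient enrolled just after one batch could be scanned, at about 12 weeks, before the next is read. Unstained slides can still ship in one batch at the end.
4. **Restrict replacement.** Decide it on that read alone, before the patient's first response scan and while accrual is open, and for the tissue analyses only. The replaced patient, if dosed, stays in the ORR. State whether 49 is a ceiling.
5. **If the read cannot be moved,** delete the replacement sentence.

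The cost is amendment wording and a few extra slide shipments or scans. The same review is done, only earlier.

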### Biological Material Submission

1. Available hematoxillin and eosin stained slides for pathology review
2. Tumor tissues from a primary melanoma excisional biopsy specimen or from a metastatic lesion
  - a. A paraffin-fixed, formalin-embedded tumor block, or
  - b. 16 unstained slides at 10micron and 10 unstained slides at 5 micron
3. Blood samples (see Section 9.3)
4. Stool samples (see Section 9.4)
5. (Optional) On-treatment fresh tumor biopsies at baseline and at 6-8 weeks of therapy

**NOTE:** An informed consent MUST be signed prior to the submission of any material for any correlative study, including mandatory diagnostic reviews.

**NOTE:** Appendix A and B must be submitted with each specimen submission at the end of the study. All samples, sample treatments, and collection time points are to be indicated on the form(s). Appendix A and B should accompany the samples to the central laboratory. Appendix C must be submitted with on-treatment biopsy specimens.

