**Documenting the number of doses of ipilimumab and nivolumab combination and nivo monotherapy**
- 5) **Toxicity Form listing Grade 3, 4 SAEs and Grade 2-4 iRAEs on each subject (within 12 weeks of decision to stop treatment)**
- 6) **Follow-up Form** (every 3 months)
- 7) **Pathology** (submitted along with pathology specimens at end of patient treatment)
- 8) **Off-Treatment Form** (within 2 weeks after treatment terminates)

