**Appendix F**  
**Suggested Schedule of Events**

Assessment 6 wks = 1 cycle	Baseline	Induc- tion			Maintenance	End of Treatment	Disease Progression	Follow-up/ Safety Follow-up
	Within 4 weeks	Cycle 1	Cycle 1	Cycle 2	Cycle 3 and after			
		Day 1	Day 22	Day 1	Day 1			
Informed consent	x							
Assignment identification numbers	x							
Medical history and demographics e	x							
Complete physical exam	x							
Weight	x							
Height	x							
ECOG performance status	x					x	x	x
Hematology&Chemistry lab c,d	x		x	x	x	x	x	
Adverse events			x	x	x	x	x	x
Imaging Studies a	x a				x a			x a
Submission of Archival tumor for review	x							
Fresh tumor biopsy				x b				
Peripheral blood correlates	x	x		x	x			
Microbiota correlates		x	x				x	

a. Non-CNS Imaging should include a chest, abdomen and pelvis CT. Imaging of other sites should be obtained when clinically indicated. If follow up scans

Protocol Number: CA209763

Version dated: January 31, 2019

indicate partial or complete response, a repeat confirmatory scan should be obtained within 12 weeks (but no sooner than 6 weeks). Baseline imaging should be done within 4 weeks prior to registration, then every 12 weeks if patient is < 2 years from study entry, then every 6 months (+/- 4 weeks) until 5 years from study entry

- b. Fresh tumor biopsy is expected in 25% of patients (N=25; 10 MCM and 5 ALM patients) to consent to on-treatment biopsies. Please refer to appendix G for detail. This can be collected within weeks 6-8.
- c. Hematology Labs should include CBC with differential (hemoglobin, hematocrit, white blood cells, platelets, neutrophils, lymphocytes, eosinophils and monocytes)
- d. Chemistry Labs should include albumin, amylase, lipase, BUN, creatinine, ALT, AST, LDH, serum alkaline phosphatase, direct and total bilirubin, glucose, total protein, sodium, potassium, chloride, HCO3, calcium, uric acid and CPK. Labs should also include TSH and free T4 if TSH is elevated. Sites should follow their institutional guidelines for hematology and Chemistry labs.
- e. Updated history and limited physical examination are recommended to be performed every 3 weeks for the first two cycles, then on the first day of subsequent cycles.

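### Treated mucosal melanoma patients leave the primary response-rate analysis if tissue is not submitted, although the endpoint uses no tissue result, and no all-treated response rate is planned

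*Combined protocol and SAP*

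**What the plan says.** Section 2.1 makes the primary objective the investigator-assessed RECIST 1.1 objective response rate (ORR) in MCM. Section 10.2 tests it by exact binomial against a null of at most 25%, one-sided at 10%. It asks for 39 patients for 90% power at a true 45%, raised to 49 for a 20% non-evaluable or dropout rate.

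Sections 10.1 and 10.2 give two grounds for being unevaluable, joined by an 'or'. One is not receiving the combination. The other is missing tissue. Section 10.1 says of patients on either ground: "therefore cannot be classified into a predictive factor group, will be deemed unevaluable for the primary endpoint of the study". Section 10.2 applies the same rule to "those for whom tissue is not submitted (see section 9.0) and therefore cannot be classified into a predictive factor group". Such patients "will be deemed unevaluable for the primary endpoint of the study; available information on these patients will be described in the final report".

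Section 10.1 has a separate replacement rule. Patients whose block is not received by the tissue bank, or is not evaluable "due to insufficient tumor on the block, will be replaced".

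Section 10.3.1 calculates ORR by cohort with an exact 95% interval and names no all-treated denominator. Its sentence about all enrolled patients concerns hypothesis-generating biomarker associations.

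The time of submission is stated in several ways:
- Appendix F has a baseline entry: "Submission of Archival tumor for review".
- Section 11.0 lists a pathology form "submitted along with pathology specimens at end of patient treatment".
- The material list in Section 9.1 says "Appendix A and B must be submitted with each specimen submission at the end of the study".
- Section 9.2.1 says "At the end of the study, all samples, including on-treatment biopsy samples, at participating institution will be batched and shipped".
- A footnote in Appendix G gives both the end of each patient's therapy and the end of the trial.

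**The concern.** The reason given for the exclusion, that the patient cannot be placed in a predictive factor group, belongs to the biomarker analyses. No such group enters the ORR test. The rule therefore removes dosed patients with a known RECIST response from the denominator because of a specimen-handling step.

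The trial is single-arm and unblinded, and this is its only formal hypothesis test. If submission is settled at baseline, the exclusion is fixed before any response is seen. If it is settled at the end of treatment or of the study, it can follow the first response reading at about week 12 (Section 5.2), and possibly the primary analysis at 6 months (Section 10.2). The plan does not define when tissue counts as submitted, so it does not say which applies.

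Loss weighted to non-responders makes the test too lenient; loss weighted to responders makes it too strict. A promise to describe the excluded patients is not a pre-specified analysis that would reveal either. The replacement rule adds a further gap. It does not say whether replaced patients' responses leave the ORR, or how replacement fits with the inflation from 39 to 49.

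**Working it through.** **Inputs.** From Section 10.2: null ORR 25%, alternative 45%, one-sided level 10%, 39 evaluable, 20% allowance, 49 enrolled, exact binomial. The plan gives no number of tissue losses and no response rate among those lost, so every loss pattern below is an assumption.

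**Plan's own figures.** The cut-off c(n) is the smallest r with P(X ≥ r | n, 0.25) ≤ 0.10. For n = 39, c = 14, type I error is 0.0862 and power at 45% is 0.9048. For enrolment, 39/0.8 = 48.75, so 49. The sample size reproduces.

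**Cut-offs for other n.**

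| n analysed | cut-off |
|---|---|
| 40 to 43 | 15 |
| 44 to 46 | 16 |
| 47 to 49 | 17 |

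At n = 49 the type I error is 0.0836 and power is 0.9458.

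**(a) 49 treated, cut-off reset to the number left.**

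If k non-responders are lost, the test rejects when X ≥ c(49 − k), with X from Bin(49, 0.25):

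| k lost | rejects at | type I error |
|---|---|---|
| 0 to 2 | ≥ 17 | 0.0836 |
| 3 to 5 | ≥ 16 | 0.1424 |
| 6 to 9 | ≥ 15 | 0.2253 |

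If k responders are lost, it rejects when X ≥ c(49 − k) + k:

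| k lost | rejects at | type I error | power at 45% |
|---|---|---|---|
| 1 | ≥ 18 | 0.0456 | 0.9052 |
| 2 or 3 | ≥ 19 | 0.0231 | 0.8460 |

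Single results can turn either way:
- 16/49 fails (p = 0.142), but with three non-responders removed 16/46 succeeds (p = 0.090).
- 17/49 succeeds (p = 0.084), but with one responder removed 16/48 fails (p = 0.123).

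**(b) Patients replaced until 39 are evaluable, success at ≥ 14/39.** If a fraction f is lost, all of them non-responders, the analysed ORR at the null is 0.25/(1 − f):

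| f | analysed ORR | P(X ≥ 14) |
|---|---|---|
| 0.02 | 0.2551 | 0.0988 |
| 0.05 | 0.2632 | 0.1212 |
| 0.10 | 0.2778 | 0.1694 |
| 0.20 | 0.3125 | 0.3192 |

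The last row is an extreme bound, because the plan's 20% also covers patients never dosed and dropouts.

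In the other direction, suppose 10% of responders and 3.3% of non-responders are lost, which is 5% overall at the null. The analysed ORR is 0.25 × 0.90/0.95 = 0.2368, with type I error 0.0587. At a true 45% it is 0.4324, with power 0.8619.

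**(c) Milder, random loss from 49 treated.** Let λR and λN be the loss rates in responders and non-responders, a = 0.25(1 − λR) and b = 0.75(1 − λN). The number left is m ~ Bin(49, a + b), and the type I error is Σ P(m) · P(Bin(m, a/(a + b)) ≥ c(m)).

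| overall loss | only non-responders lost | non-responders lost at twice the responder rate |
|---|---|---|
| 5% | 0.108 | 0.087 |
| 10% | 0.159 | 0.107 |
| 20% | 0.288 | 0.145 |

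**(d) Loss unrelated to response.** The analysed ORR stays at the true value, so the test keeps its level by construction. At 39 evaluable it keeps 8.6% and 90% power.

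**The case against.** The strongest reply is that the clause will rarely bite. Adequate tissue is required by 3.1.3, its lack is an exclusion under 3.21 and 3.24, and Section 4.0 has eligibility confirmed before registration. Section 9.2.1 then keeps the slides at the institution. What remains is a treated patient whose confirmed tissue is never submitted. With random and only moderately selective loss, the error stays near 10% until losses are heavy, as (c) shows. One lost responder still leaves power above 90%. Nor does the plan say that replacement continues until 39 are evaluable. All of this stands, and it is why the figures are ranges and bias is not asserted.

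It may also be said that the timing passages mix collection, forms and batch shipping, and that Section 9.2 has tissue collected at baseline. That is a fair reading, but the text does not settle it. Section 9.1 speaks of specimen submission at study end, and receipt by the tissue bank can only follow shipment.

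Central review of the diagnosis (Section 9.2.1) also needs tissue, but nothing says that review changes the ORR denominator.

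Lastly, Section 10.3.1 does not name a tissue-based denominator. It does not need to, because Sections 10.1 and 10.2 already declare these patients unevaluable for the primary endpoint.

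The plan itself provides for blocks that are not received or hold too little tumor, so the case is foreseen. Stating the rule in advance does not make it suit the endpoint.

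**Conclusion.** The concern holds. As written, the plan removes dosed MCM patients from the primary ORR on a ground that plays no part in that endpoint, and it plans no ORR that keeps them.

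The effect depends on how many are lost and who they are, and the documents show neither. If 49 are treated and the cut-off is reset to the number left, one or two lost non-responders have no effect. Three to five raise the type I error to 14.2%, above the planned 10%. Lost responders make the test stricter and cost power. Loss unrelated to response is harmless to the error rate. The entry check makes small numbers plausible. The point should be fixed because it touches the only formal test and the remedy is cheap, not because bias has been shown.

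**What to change.** In Sections 10.1 and 10.2:

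- Define the cohort A primary set as all enrolled MCM patients who meet the non-tissue eligibility criteria and receive at least one dose of the combination, whatever happens to their tissue later. State that 3.1.3, 3.21 and 3.24 apply at registration only.
- Count treated patients with no post-baseline assessment as non-responders.
- Delete the tissue clause from the rule on who is unevaluable for the primary endpoint. Confine tissue-based replacement and the tissue-evaluable set to the biomarker analyses, and report ORR in that set as a sensitivity analysis.
- State the exact cut-off for the number treated: for 49, at least 17 (type I error 8.4%, power 94.6% at 45%); for 46, at least 16 (9.0%); for 43, at least 15 (9.6%).
- Say that the 20% inflation, not replacement, covers losses for the primary endpoint.
- Define when tissue counts as submitted, and reconcile Sections 9.1, 9.2.1 and 11.0 with Appendices F and G.

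The cost is wording, one sensitivity analysis, a restated cut-off and one agreed submission time; no patients are added. The downside is a possibly lower ORR and power if the patients brought back are mainly failures. If 5%, 10% or 20% of the 49 are all failures and the rest respond at 45%, the ORR is 0.45 × 0.95 = 42.8%, 0.45 × 0.90 = 40.5% or 0.45 × 0.80 = 36.0%. Power at ≥ 17/49 is then 90%, 83% or 63%.
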